### 5.1.2.3 Multiple imputations for response variables

PASI 75 and IGA 0 or 1 response at Week 12 will be evaluated using an exact logistic regression model with treatment group baseline body weight stratum, age stratum and

baseline PASI as effects with multiple imputations for missing values. In addition, exact logistic regression analysis for PASI 50, PASI 75, PASI 90, PASI 100 and IGA mod 2011 0 or 1 response by visits will be analyzed using multiple imputation method.

Summary statistics for PASI 50, PASI 75, PASI 90, PASI 100, and IGA mod 2011 0 or 1 response by visit will be presented in contingency tables with multiple imputations method.

In the multiple imputations analysis, the response status will be imputed based on the individual treatment arm information.

In case of higher drop-out rates or higher study treatment discontinuations for reasons other than lack of efficacy, additional sensitivity analyses will be performed.

Multiple imputation (MI) is a simulation based approach where missing values are replaced by multiple Bayesian draws from the conditional distribution of missing data given the observed data and covariates, creating multiple completed data sets. These completed data sets can then be analyzed using standard methods. [Rubin \(1987\)](#) presented rules how to combine the multiple sets of estimates to produce overall estimates and confidence intervals that adequately incorporate missing data uncertainty.

Missing values for the 'PASI score', 'IGA mod 2011 score', 'change from baseline PASI score' and 'change from baseline IGA score' will be imputed simultaneously based on an underlying normal distribution and using a Markov Chain Monte Carlo (MCMC) method. The change from baseline in PASI score appears to follow closer to a normal distribution than the actual PASI score. Assuming normality for the 'IGA mod 2011 score' is motivated by [Schaefer \(1997\)](#), where it was shown that the multivariate normal approximation for the imputation of incomplete categorical and binary data is robust.

The imputations will be done separately for each treatment group including baseline weight, and number of previous systemic therapies as additional covariates.

The number of imputations will be set to 100, the seed for the random function will be set to 4572310 for this study. To generate the multiple imputed data sets, the SAS procedure MI can be used as follows:

The input data set <pasi\_iga> should have one record per subject with baseline PASI and baseline IGA mod 2011 score as well as all post-baseline IGA and PASI score and all changes from baseline in PASI and IGA scores. Baseline weight and number of previous systemic therapies should also be included in the input data set. Of note, baseline IGA scores will not be considered due to almost all subjects having IGA score = 4.

```
ODS LISTING CLOSE;
ODS OUTPUT MissPattern=msgpat VarianceInfo=varinfo ParameterEstimates=param;
PROC MI DATA=<pasi_iga> OUT=<impdata> SEED=457<studycode> NIMPUTE=100 EM converge=1E-2 maxiter=300000;
  <MCMC prior=RIDGE=2>;
  VAR <baseline weight> < >
    <number of previous systemic therapies>
    <baseline PASI> < >
    <change from baseline PASI week1> - <change from baseline PASI week primary endpoint>
    <IGA week 1> - <IGA week primary endpoint>;
  BY <treatment group>;
  RUN;

ODS LISTING;
```

Programming notes:

- For MCMC option in MI procedure start with `<MCMC prior=RIDGE=2;>` option. If model converges and no error, then continue with other steps. Otherwise if “prior=RIDGE=2” option does not work then split PROC MI processing into 2 parts, one part with PASI related variables another part with IGA Mod related variables.  
This this approach doesn't work then updated “prior=RIDGE” with “prior=JEFFREYS” option in the above model.
- The SAS procedure MIANALYZE expects a variable called “\_IMPUTATION\_” which is generated by the MI procedure. It might be needed to set the SAS option “VALIDVARNAME=UPCASE” temporarily in the program before the MI call, this option should be reset after the MIANALYZE call to VALIDVARNAME=V6.
- In case there are none missing in one treatment group, the MI procedure does not impute any values. In this case the corresponding data need to be imputed manually outside PROC MI and added to the dataset `<impdata>`.

The imputed data are saved in data set `<impdata2>`. The outcome of interest, i.e. the PASI 75 and IGA 0 or 1 response will be calculated, e.g. as follows:

```
DATA <impdata2>;
  SET <impdata>;
  IF <change from baseline PASI week primary endpoint>/<baseline PASI>=0.75 THEN <PASI 75 response> =1;
  ELSE <PASI 75 response>=0;
  <...repeat for all PASI response...>

  IF <baseline IGA> >=3 THEN DO;
    IF <IGA per week primary endpoint> < 1.5 THEN <IGA 0/1 response> =1;
    ELSE IF <IGA per week primary endpoint> >=1.5 THEN <IGA 0/1 response> =0;
    ELSE PUT "E" "RROR:" stysid1a=;
  END;
  ELSE IF <baseline IGA>=2 THEN DO;
    IF <IGA per week primary endpoint> < 0.5 THEN <IGA 0/1 response> =1;
    ELSE IF <IGA per week primary endpoint> >=0.5 THEN <IGA 0/1 response> =0;
    ELSE PUT "E" "RROR:" stysid1a=;
  END;
  ELSE <IGA 0/1 response> =0;
RUN;
```

The treatment differences for each imputed data set will then be evaluated by exact logistic regression and ODDS ratio as described in [Section 5.1.2.2](#). This analysis will be done by `_IMPUTATION_` for the comparison to the placebo treatment group. The model should be estimating response probability = 1 by using DESECENDING option. Using the EXACT statement in the GENMOD procedure and the ODS OUTPUT data set “ExactOddsRatio” provides the exact estimate for the odds ratio and confidence intervals.

```
PROC GENMOD <option>;
  CLASS <stratum> <treatment>(ref="")/ param=ref;
  MODEL <response> = <explanatory variables> / link=logit dist=bin type3;
  BY <by-variables>;
  EXACT <treatment>/ ESTIMATE=both ;
  ODS OUTPUT ExactOddsRatio =Estimates;
RUN;
```

The MIANALYZE procedure expects the parameter estimate in the variables ESTIMATE. No standard error estimate for odds ratio will be provided in “Estimates” dataset.

```
Data <modified dataset>;
```

```
set Estimates;
ESTIMATE=Estimate;

if missing(ESTIMATE) then delete;
RUN;
```

The estimates and standard errors of the log (odds ratio) based on the 100 imputed data are then combined by applying Rubin's rules for multiple imputed data sets, see [Little and Rubin \(2002\)](#).

Programming notes:

- The variables ESTIMATE in the input data set for the MIANALYZE procedure may not be missing. Records with missing values need to be deleted and the variable \_IMPUTATION\_ needs to be renumbered and regenerated since for each by group the procedure expects consecutive numbers starting at 1.
- The ESTIMATE and STDERR in terms of odds ratios from logistic regressions will be transformed to follow a normal distribution before MIANALYZE procedure. They will be transformed back to Odds Ratio to get the corrected ESTIMATE and corresponding CIs.

The SAS procedure MIANALYZE will be applied as follows:

Step 1:

```
DATA <modified dataset_t>;
SET <modified dataset>;
stderr= stderr;
VARIABLE="estimate";
RUN ;

ODS LISTING CLOSE;
ODS OUTPUT ParameterEstimates=<results> VarianceInfo=<varinfo> ModelInfo=<modelinfo>;
PROC MIANALYZE PARMS=<modified dataset>;
BY <by-variables>;
MODELEFFECTS ESTIMATE;
RUN;

ODS LISTING;
data <results_back>;
set <results>;
estimate=exp(ESTIMATE);
LCLMEAN=estimate*exp(-1.96*stderr);
UCLMEAN=estimate*exp(+1.96*stderr);
RUN ;
```

In case if exact logistic regression does not converge and risk difference estimates will be provided. The SAS procedure PROC FREQ for risk difference estimates will be applied as follows:

```
ODS LISTING CLOSE;
PROC FREQ DATA=<Imputed dataset> ORDER=DATA;
  TABLES <treatment group>*<response variable>/riskdiff fisher alpha=0.05;
  BY <By-variables>;
  ODS OUTPUT RiskDiffCol1=RiskDiffCol1 FishersExact=fisherexact;
RUN;

ODS LISTING;
DATA DRISK; SET RiskDiffCol1;
  WHERE control="1";
  ESTIMATE=risk;
  STDERR=ase;
  effect="Riskdiff";
```

```
IF missing(ESTIMATE) OR missing(STDERR) THEN DELETE;  
RUN;  
  
PROC SORT DATA=DRISK; BY <By-variables>; RUN;  
ODS LISTING CLOSE;  
ODS OUTPUT ParameterEstimates=results VarianceInfo=varinfo ModelInfo=Modelinfo;  
PROC MIANALYZE PARAMS=drisk;  
  by <By-variables>;  
  modeleffects Riskdiff;  
  stderr ase;  
RUN;  
  
ODS LISTING;  
DATA results2;  
  set results;  
  or=estimate*100;  
  lowercl=(LCLmean)*100;  
  uppercl=(UCLmean)*100;  
  KEEP <response variable> <By-variables> or lowercl uppercl probt;  
RUN;
```

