| 24-Apr-2019 | Prior to week 24 DB lock | Updated exact logistic regression model information., visit window information  | Section 5.1.2.2 Exact Logistic regression
Section 2.1 Data analysis general information
Section 2.1.1.5 Visit windows
Section 2.6.4 Handling of missing values/censoring/discontinuations
Section 2.9.1.1 Adverse events of special interest / grouping of AEs   |
| 30-APR-2019 | Prior to week 24 DB lock | Updated table 1-1 information for W24PEA, updated data analysis general section, updated table 2-1, added table 2-2b,   | Section 1 Induction
Section 1.2 Study objectives and endpoints
Section 2.1.1.1 Study treatment
Section 2.6.3 Statistical hypothesis, model, and method of analysis
Section 2.9.1 Adverse events (AEs)  |
| 01-MAY-2019 | Prior to week 24 DB lock | 2.14 Growth and Physical development
2.15.5 Interim analysis
4 Change to protocol specified analyses
5.1.2.2 Exact Logistic regression -exact logistic regression model related details.
Table 5.1 Time to event: definition of risk set, | Section 2.14 Growth and Physical development
Section 2.15.5 Interim analysis
Section 4 Change to protocol specified analyses
Section 5.1.2.2 Exact Logistic regression -exact logistic regression model related details.
Section 5.1.5 Analysis of time-to-event data
Section 2.9.3 Laboratory data |

| Date        | Time point                             | Outcome for update  | Section and title impacted
(Current) |
|-------------|--|---|---|
|             |  | timing and censoring by variable - updated ConMed censoring details.  |   |
|             |  | Table 2-13 CTCAE grades for laboratory parameters to be analyzed, for eGFR related update                               |   |
| 04-MAY-2019 | Prior to week 24 DB lock               | Updated the reference section   | Section 6 Reference                     |
| 02-Aug-2019 | After DB lock                          | MI section remove “baseline IGA score and failure to at least one previous biologic (yes/no)” from the PROC MI section. | Section 5.1.2.3                         |
| 06-Aug-2019 | After DB lock                          | [REDACTED]  | Section 2.10                            |
|             |  | [REDACTED]  | Section 5.6.1                           |
|             |  | Updated CDLQI scoring related details.  |   |
|             |  | Added extended Week 12 visit window details   | Section 2.1.1.5                         |

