### 1.1 Study design

This is a multicenter, randomized, double-blind, placebo-and active-controlled (etanercept in single blinded arm) study in pediatric subjects aged 6 years to less than 18 years with severe chronic plaque psoriasis. Approximately 160 subjects aged 6 years to <18 years will be enrolled, of which at least 30 pediatric subjects will be 6 years to <12 years old. In reality around 40-45 patients will be needed to meet the requirement of recruiting about 30% of subjects in the < 25kg weight group.

Subjects will be randomized using a 1:1:1:1 ratio into one of the treatment arms: secukinumab low dose, secukinumab high dose, etanercept or placebo. The randomization will be stratified by age (<12 years or ≥12 years) and weight (<25 kg, 25-<50 kg, ≥50kg) at randomization. Subjects randomized to the placebo group will be pre-assigned to either the low- or high-dose group of secukinumab, at the Randomization visit, in case they are not achieving a PASI 75 response as assessed at Week 12.

The study consists of 5 Epochs: screening (up to 4 weeks), induction (of 12 weeks), maintenance (of 40 weeks), extension treatment epoch (open-label of 184 weeks) and post-treatment follow-up epoch (of 16 weeks). The detailed information of the study design is described in [Figure 1-1](#).

**Figure 1-1** Study design

The following study periods will be considered for analysis:

- **Screening period** (before Randomization)
- **Induction period** (Randomization to Week 12 pre-dose), including follow-up period (F4, F8, F12 and F16 (EOF) visits) for prematurely discontinued subjects before Week 12 completion. For placebo PASI 75 responders at Week 12, subjects will enter follow-up period after Week 12, including the first visit F4 and four weeks later visit EOF at F8.
- **Maintenance period** (Week 12 dose to Week 52 pre-dose), including follow-up period (F4, F8, F12 and F16 visits) for prematurely discontinued subjects before Week 52 completion, and for etanercept patients with the completion of the maintenance epoch.
- **Extension period** (Week 52 dose until Week 236 (EOT)), including follow-up period (F4, F8, F12 and F16 visits) for prematurely discontinued subjects before Week 236 completion.
- **Entire treatment period** (Randomization to Week 236 (EOT)), for safety analysis, exposure including follow-up period up to last dose + 84 days.
- **Entire study period** (Randomization to end of study (EOS)), including follow-up period (F4, F8, F12 and F16 visits).

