**Table 2-6 Subgroup analyses**

| Endpoint/analysis                   | Randomization strata including age and weight | Previous psoriasis therapy* |
|-------------------------------------|---|-----------------------------|
| PASI 75/90 response @ Week 12       | X   | X                           |
| IGA mod 2011 0/1 response @ Week 12 | X   | X                           |
| Adverse event                       | X   |                             |

Note: presented are only those endpoints that need subgroup analyses.

\*: only for “Previous < systemic > therapy” and embedded subgroup “failure”.

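### The multiple-imputation model omits the age stratum, so it is narrower than the primary model it feeds and can blur differences between the age groups

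*SAP*

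**What the plan says.** SAP 2.6.4 makes multiple imputation the primary method for missing PASI and IGA responses up to Week 52. SAP 5.1.2.3 describes the imputation model in three places:

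- The covariate sentence: imputation is run by treatment group, "including baseline weight, and number of previous systemic therapies as additional covariates".
- The input data set: "Baseline weight and number of previous systemic therapies should also be included in the input data set", alongside the PASI and IGA data.
- The PROC MI VAR list: baseline weight, number of previous systemic therapies, baseline PASI, PASI changes by week and IGA scores by week.

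None of the three names age. The VAR list also contains two empty brackets. They match in number the two variables that the SAP document history records as removed from PROC MI on 02-Aug-2019: baseline IGA and failure of a previous biologic. Neither of these is age.

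Age has a role in three other places:

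- Randomisation (SAP 1.1): "The randomization will be stratified by age (<12 years or ≥12 years) and weight".
- The analysis model. The opening sentence of SAP 5.1.2.3 itself lists "treatment group baseline body weight stratum, age stratum and" baseline PASI as effects, in line with SAP 2.6.3.
- Subgroups. SAP Table 2-6 crosses Week 12 PASI 75/90 and IGA 0/1 response with "Randomization strata including age and weight".

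**The concern.** An imputation model should normally contain every variable in the analysis it feeds. Here the analysis conditions on age and the imputation does not. An imputed child under 12 therefore receives a score typical of subjects in the same arm with the same weight, treatment history and visit scores, whatever their age. If age carries further information about Week 12 response, imputed subjects in the two age groups look too alike.

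What is at stake is the age-subgroup result and the age coefficient. Children under 12 are the smaller group, and under the protocol they were enrolled only after the DMC had reviewed adolescent data. Readers will look to the subgroup table to see whether they respond as adolescents do, and any bias of this kind would favour apparent similarity. SAP 4.1 adds that a number of Week 12 visits fell after Day 88, outside the Week 12 window, so dropout need not be the only source of missing Week 12 values. It gives no count.

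**Working it through.** **The plan's own figures.** The plan quantifies nothing about age or missing data. Its only figures for the Week 12 comparison are powers from Fisher's exact test (SAP 3). With 40 per group and one-sided alpha 1.25%, exact enumeration gives:

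- 10% v 65% (PASI 75): 99.9% (stated about 99%)
- 10% v 45% (IGA 0 or 1): 88.4% (stated about 88%)
- 8% v 39% (PASI 90): 82.1% (stated about 82%)

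These figures reproduce, and they do not depend on the imputation model.

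**Inputs from the documents.** SAP 1.1 expects about 40–45 subjects under 12 out of about 160, allocated 1:1:1:1. That is 40/160 = 25% to 45/160 = 28%, and 40/4 = 10 to 45/4 = 11 per arm.

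**Assumed inputs.** The documents give no missing fraction, age effect or age–weight correlation. The main simulation took one large arm (300,000 subjects) with:

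- 25% under 12
- an age effect of 0.5 SD, about 16 points in response
- visit-to-visit correlation 0.8
- 5%, 10% or 20% missing at random
- missingness patterns from the Week 12 score alone to little or no earlier visit information

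Imputation was by normal regression on weight, previous therapies and earlier visits, as an approximation to the SAP's MCMC model.

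**Formula.** Only the missing fraction m is imputed, so

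loss in age difference ≈ m × (true difference − difference among imputed subjects).

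Examples at age–weight correlation 0.6:

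- m = 20%, little earlier information: 0.20 × (16.2 − 4.1) = 2.4 points
- m = 10%, least earlier information: 0.10 × (16.4 − 5.0) = 1.1 points
- m = 5%, little earlier information: 0.05 × (16.0 − 5.2) = 0.5 points

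**Results with the age stratum omitted.**

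| Missing | Loss, age–weight correlation 0.6–0.8 |
|---|---|
| 5% | 0.1–0.6 points |
| 10% | 0.4–1.1 points |
| 20% | 0.5–2.4 points |

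- Among imputed subjects only, the 16-point difference falls to about 4–13 points.
- If weight carried no information on age, the loss at 20% missing would reach 16.2 − 12.9 = 3.3 points.
- With the age stratum added, the difference returns to 15.8–16.6 points.
- If age acts only through weight (10% missing), the difference goes from 16.1 to 16.1 at correlation 0.8 and from 12.3 to 12.2 at 0.6.
- The arm's overall response rate is about 69% before and after imputation and moves by at most 0.2 points.

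**Second simulation at trial size.** This used 40 per arm, 28% under 12, correlation 0.6 and 4000 simulated arms per setting. Without age, the difference went from 18.8 to 18.4 (5% missing), 19.1 to 18.3 (10%) and 18.7 to 17.2 (20%), losses of 0.4, 0.8 and 1.5 points. With age, it went from 18.8 to 18.7, 18.5 to 18.4 and 18.7 to 18.5.

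The starting difference itself varies by several tenths of a point between settings, so the 5% figures show only an order of magnitude.

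**The case against.** A reader might infer that the imputed values necessarily draw the age groups together. The documents do not support that. Continuous baseline weight is in the model, and in subjects aged 6 to under 18 it is a natural proxy for age. Baseline PASI and the PASI and IGA scores at earlier visits are there too. No residual age effect beyond these is shown anywhere, and without one there is no material shrinkage. The upper figure of 2.4 points needs 20% missing by Week 12, which nothing in the documents indicates.

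A reader might also infer that the primary test is biased. It is hardly touched: imputation is by arm, the arm rates do not move materially, randomisation was stratified by age and no hypothesis concerns an age difference. SAP 2.6.5 already repeats the co-primary and key secondary analyses with non-responder imputation, which does not use this model.

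Nor do the documents say that the age-subgroup tables use these imputations. Table 2-6 and the subgroup note in SAP 5.1.2.2 name no method. Multiple imputation is a fair inference from its primary status in SAP 2.6.4. However, the age-stratum figure in SAP 4.1 that excludes subjects affected by the dosing error uses non-responder imputation.

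Finally, adding a term has a cost. The VAR list already holds 3 baseline variables plus 6 PASI changes and 6 IGA scores, 15 in all, for about 40 subjects per arm, and the SAP plans for fitting failure.

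All of this limits the size and certainty of the effect. It does not explain the omission: the SAP gives a reason for leaving out baseline IGA and none for leaving out age.

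**Conclusion.** The omission is real. By the SAP's own description the imputation model is narrower than the primary model and the subgroup analyses. The empty brackets do not change this, because the covariate sentence and the input-data sentence do not name age either.

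The consequence is conditional and small. If age predicts response beyond weight, baseline PASI and the earlier visits, age-group differences of about 16 to 19 points lose roughly 0.1 to 2.4 points at 5% to 20% missing with weight as a proxy. If age works only through weight, the loss is negligible. The age effect, age–weight correlation, visit correlation and missing fraction behind this range are all assumptions. That the subgroup tables are affected assumes that they use multiple imputation.

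The treatment comparison is barely affected. For that, the simulation checked the arm's response rate, not the age-adjusted odds ratio; the rest follows from by-arm imputation and stratified randomisation. This is an inexpensive improvement and does not threaten the trial's conclusions.

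**What to change.** Add the age stratum (0/1) to the covariate sentence, the input data set and the PROC MI VAR list in SAP 5.1.2.3. State, in Table 2-6 or the subgroup note in SAP 5.1.2.2, that the age-subgroup tables use this imputation. Delete or fill the two empty brackets in the VAR list.

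The current SAP is dated 18-Dec-2020, before the Week 104 lock and after the Week 24 and Week 52 cut-offs (7 March and 18 September 2019). For those locked analyses, leave the primary result as it stands and report the age-included imputation as an additional sensitivity analysis under SAP 4.1.

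The cost is a sixteenth variable in a by-arm model of about 40 subjects, roughly 10 of them under 12, plus the rerun. The ridge prior, the option to split PASI from IGA and the Jeffreys fallback already in the SAP can accommodate it. The stratum is already collected.

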§ Buttocks are assessed as part of the Lower limbs (L) body region.

The following definitions are possible efficacy evaluations that will be used in clinical trials in psoriasis ([CHMP/EWP/2454/02, 2004](#)):

- **PASI 50 response:** subjects achieving  $\geq 50\%$  improvement (reduction) in PASI score compared to baseline are defined as PASI 50 responders
- **PASI 75 response:** subjects achieving  $\geq 75\%$  improvement (reduction) in PASI score compared to baseline are defined as PASI 75 responders
- **PASI 90 response:** subjects achieving  $\geq 90\%$  improvement (reduction) in PASI score compared to baseline are defined as PASI 90 responders
- **PASI 100 response / remission:** complete clearing of psoriasis (PASI=0)

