#### **2.9.3 Laboratory data**

The summary of laboratory evaluations will be presented for three groups of laboratory tests (hematology, clinical chemistry and urinalysis). All laboratory data will be listed with "on-treatment" flag displayed.

For urinalysis, frequency tables will be presented.

The general guideline for laboratory summaries (hematology and clinical chemistry) is as below:

- All the summary of lab outputs (newly occurring or worsening notables, maximum changes, shift tables, by visit summary statistics) will consider the "on-treatment" data. i.e., all assessments within last dose plus 84 days.

Descriptive summary statistics for the change from baseline to each study visit will be presented. These descriptive summaries will be presented by laboratory test and treatment group. Change from baseline will only be summarized for subjects with both baseline and post baseline values and will be calculated as:

$$\text{change from baseline} = \text{post baseline value} - \text{baseline value}$$

The laboratory test values below the Lower Level of Quantification (LLQ) or above the Upper Level of Quantification (ULQ) will be imputed as LLQ or ULQ values, respectively. The numerical part of the reported result will be treated as the actual LLQ or ULQ. These laboratory values will be displayed in listings using the standard unit with the reported sign (“<” or “>”).

In addition, shift tables will be provided for all parameters to compare a subject's baseline laboratory evaluation relative to the most extreme laboratory test value within a treatment period. For the shift tables, the normal laboratory ranges will be used to evaluate whether a particular laboratory test value is normal, low, or high (including category “high and low”). These summaries will be presented by laboratory test and treatment group. Subjects with abnormal laboratory values will be listed and values outside the normal ranges will be flagged.

The following laboratory parameters will be analyzed with respect to numerical Common Terminology Criteria for Adverse Events (CTCAE) grades, given [Table 2-13](#): hemoglobin, platelets, white blood cell count, neutrophils, lymphocytes, creatinine, total bilirubin (TBL), gamma-glutamyl transferase (GGT), alanine aminotransferase (ALT), aspartate aminotransferase (AST), alkaline phosphatase (ALP), estimated glomerular filtration rate (eGFR).

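### The SAP's example code for PASI response after multiple imputation contradicts the PASI 75 definition: under the SAP's only change-from-baseline formula, no improving child meets it

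*SAP*

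**What the plan says.** SAP 2.6.1.1, below Table 2-8, sets the rule: children with at least a 75% "improvement (reduction) in PASI score compared to baseline are defined as PASI 75 responders". Protocol 6.4.2 agrees.

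SAP 2.6.4 makes multiple imputation the primary method for missing PASI and IGA data up to Week 52, with response derived from the imputed scores. SAP 5.1.2.3 then gives code for that derivation, introduced by "The outcome of interest, i.e. the PASI 75 and IGA 0 or 1 response will be calculated, e.g. as follows". The PASI 75 condition is "IF <change from baseline PASI week primary endpoint>/<baseline PASI>=0.75 THEN <PASI 75 response> =1", followed by "ELSE <PASI 75 response>=0" for everyone else and by "<...repeat for all PASI response...>".

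The SAP writes out a formula for change from baseline in two places, 2.9.3 (laboratory data) and 2.9.4.2 (vital signs). Both subtract the baseline value from the post-baseline value. No formula or sign is given for PASI change.

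**The concern.** PASI falls as psoriasis improves, so a change computed as post-baseline minus baseline is negative for every child who gets better. The printed condition needs a positive ratio. Taken with the only formulas in the SAP, it can be met only by a child whose PASI rises by 75%.

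The operator is also in doubt. Angle brackets mark placeholders in this block, so the bracket before the equals sign may simply close the baseline PASI placeholder. The condition would then be equality with 0.75, not at least 0.75.

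The step matters because it reads the whole completed data set, including children with an observed Week 12 score. It feeds the co-primary PASI 75 tests (H1, H2) and, through the repeat instruction, the key secondary PASI 90 tests (H5, H6). The IGA lines compare the score itself with a cut-off and do not have this sign problem.

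**Working it through.** **Design figures.** SAP section 3 gives 40 children per group, a PASI 75 rate of 10% on placebo and 65% on secukinumab, and Fisher's exact test at one-sided 1.25%. Exact enumeration gives 99.9% power (stated: about 99%). The same method gives 88.4% for IGA 0 or 1 (stated: 88%) and 82.1% for PASI 90 (stated: 82%). The plan's figures reproduce.

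**Direction.** Let r = (post - baseline)/baseline. If post is below baseline, r lies between -1 and 0. The definition is (baseline - post)/baseline >= 0.75, which is r <= -0.75.

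| Baseline to Week 12 | Reduction | r | Definition | Printed, read as `=` | Printed, read as `>=` |
|---|---|---|---|---|---|
| 20 to 0 | 100% | -1.00 | responder | no | no |
| 20 to 2 | 90% | -0.90 | responder | no | no |
| 20 to 5 | 75% | -0.75 | responder | no | no |
| 40 to 12 | 70% | -0.70 | no | no | no |
| 20 to 35 | 75% rise | +0.75 | no | yes | yes |
| 24 to 50 | 108.3% rise | +1.083 | no | no | yes |

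**All readings.** Take PASI in steps of 0.1, baseline from 20 (the eligibility minimum) to 72 (the scale maximum), and every post value below baseline. In tenths, the number of pairs is the sum of the integers 200 to 720: 521 x (200 + 720)/2 = 239,660.

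| Rule | Pairs flagged |
|---|---|
| Definition in SAP 2.6.1.1 | 60,241 |
| Printed, change = post - baseline, `=` | 0 |
| Printed, change = post - baseline, `>=` | 0 |
| Printed, change = baseline - post, `=` | 131 |
| Printed, change = baseline - post, `>=` | 60,241 |
| r <= -0.75 | 60,241 |

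These counts compare rules; they are not clinical response rates. The zero does not depend on the operator. The printed line matches the definition only if PASI change is baseline minus post and the operator is also `>=`. The SAP states neither.

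**Operator.** A clear at-least test in the same block closes the placeholder and then prints its own operator: "IF <baseline IGA> >=3 THEN DO". In "ELSE <PASI 75 response>=0" the equals sign directly after the bracket can only be an assignment. Both favour equality in the PASI line. The line "ELSE IF <baseline IGA>=2 THEN DO" settles nothing: the branch above it has already taken scores of 3 or more, so for whole-number IGA scores equal to 2 and at least 2 pick the same children.

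**Scale, if the line were run literally.** At the design rates the expected counts are 0.65 x 40 = 26 against 0.10 x 40 = 4 (one-sided Fisher p about 2.5e-7). With post minus baseline, and no child worsening by 75%, they become 0/40 against 0/40 (p = 1).

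**The case against.** The best defence is that this is a template. It is introduced as an example, it uses placeholders throughout, and SAP 2.6.1.1 and protocol 6.4.2 state the rule correctly. It stands in part: the definition governs. But the block is the SAP's only operational rule for turning imputed PASI values into response, and its IGA lines supply real cut-offs (1.5 and 0.5), so it also serves as specification.

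Two further points stand as caveats. The sign is carried over from safety sections, because no formula is written for PASI. The equality may be a collision between the closing bracket and an intended `>=`, since spacing in the block is uneven: the same response variable is assigned once with a space before the equals sign and once without.

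A reader might infer that the primary analysis returned no PASI responders, or that it fell into the SAP's special handling for 0% rates. The documents do not support that. The SAP describes dry runs before the Week 24 and Week 52 locks, and the same endpoints are also analysed with pure non-responder imputation. A 0% rate in every arm would be hard to miss. Nothing shows that the template was run as printed.

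**Conclusion.** The printed derivation is wrong as a specification. Under the only change-from-baseline formulas in the SAP it classes every improving child as a PASI non-responder (0 of 239,660 improving pairs, against 60,241 under the definition), whichever operator is read. This rests on applying post minus baseline to PASI, which is the natural convention but is not stated. If PASI change were baseline minus post, the line would be right with `>=` and would catch only exact 75% improvement with `=` (131 pairs). The equality reading is likely, not certain.

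The fault covers the PASI responses behind H1, H2, H5 and H6. It is a correctable contradiction between code and definition, and it is not evidence that any executed program or reported result was wrong. The current SAP amendment (December 2020) postdates the Week 24 and Week 52 data cut-offs in March and September 2019. For those analyses the correction therefore clarifies the record and calls for confirmation.

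**What to change.** State in SAP 2.6.1.1 that change from baseline in PASI is post-baseline minus baseline, so that negative values mean improvement. Then replace the PASI lines in 5.1.2.3, writing `chg12` for the Week 12 PASI change and `pasi0` for baseline PASI:

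- PASI 75: `if not missing(chg12) and pasi0 > 0 and chg12/pasi0 <= -0.75 then pasi75 = 1;`
- PASI 50 and PASI 90: the same line with -0.50 and -0.90.
- PASI 100: `pasi0 + chg12 <= 0`, with both values non-missing.

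The rule should use the change variable, because that is what the printed PROC MI variable list imputes. The list does not include post-baseline PASI, although the text of 5.1.2.3 names it among the imputed quantities. Under that code, a rule based on the Week 12 PASI score would find it missing for exactly the imputed children and score them as non-responders. The guard is needed because SAS ranks a missing number below every value: an unguarded at-or-below test would turn missing data into responders.

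Add a check that derived status equals observed status for every child with an observed Week 12 PASI. Document that code already executed followed the definition in 2.6.1.1.

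The cost is a few corrected code lines, one sentence, one programming check and a note to file. Design, alpha and data collection are unaffected.
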